14.2 STUDY RECORDS RETENTION

Study documents should be retained for a minimum of 2 years after the last approval of a marketing application in an ICH region and until there are no pending or contemplated marketing applications in an ICH region or until at least 2 years have elapsed since the formal discontinuation of clinical development of the drug combination studied in this protocol. No records will be destroyed without the written consent of the sponsor, if applicable.

14.3 PROTOCOL DEVIATIONS

A protocol deviation is any noncompliance with the clinical trial protocol, GCP, or MOP requirements. The noncompliance may be either on the part of the participant, the investigator, or the study site staff. As a result of deviations, corrective actions are to be developed by the site and implemented promptly.

These practices are consistent with ICH E6:

- 4.5 Compliance with Protocol, sections 4.5.1, 4.5.2, and 4.5.3
- 5.1 Quality Assurance and Quality Control, section 5.1.1
- 5.20 Noncompliance, sections 5.20.1, and 5.20.2.

It is the responsibility of the site to use continuous vigilance to identify and report deviations as defined by the Moffitt Clinical Trials Office standard. All deviations must be addressed in study source documents. Protocol deviations must be sent to the local IRB per their guidelines. The site PI/study staff is responsible for knowing and adhering to their IRB requirements.

14.4 PUBLICATION AND DATA SHARING POLICY

The International Committee of Medical Journal Editors (ICMJE) member journals have adopted a clinical trials registration policy as a condition for publication. The ICMJE defines a clinical trial as any research project that prospectively assigns human subjects to intervention or concurrent comparison or control groups to study the cause-and-effect relationship between a medical intervention and a health outcome. Medical interventions include drugs, surgical procedures, devices, behavioral treatments, process-of-care changes, and the like. Health outcomes include any biomedical or health-related measures obtained in

patients or participants, including pharmacokinetic measures and adverse events. The ICMJE policy, and the Section 801 of the Food and Drug Administration Amendments Act of 2007, requires that all clinical trials be registered in a public trials registry such as ClinicalTrials.gov, which is sponsored by the National Library of Medicine.

The PI will provide to the Protocol Information Specialist at Moffitt Cancer Center, details as requested for registering and reporting results for this clinical trial on ClinicalTrials.gov. At the conclusion of the trial, the PI will make study results available to the research community and the public-at-large.

Authorship in publications will be determined by the PI depending on participation, enrollment, and significant contribution during trial process and manuscript elaboration.

15 STUDY ADMINISTRATION

15.1 STUDY LEADERSHIP

Not Applicable

16 CONFLICT OF INTEREST POLICY

The independence of this study from any actual or perceived influence, such as by the pharmaceutical industry, is critical. Therefore any actual conflict of interest of persons who have a role in the design, conduct, analysis, publication, or any aspect of this trial will be disclosed and managed. Furthermore, persons who have a perceived conflict of interest will be required to have such conflicts managed in a way that is appropriate to their participation in the trial. The study leadership and the Moffitt Cancer Center have established policies and procedures for all study group members to disclose all conflicts of interest and will establish a mechanism for the management of all reported dualities of interest.

APPENDIX

Appendix A

iwCLL Criteria to Initiate Treatment of CLL (Reference #14)

- c. Evidence of progressive marrow failure manifested as worsening anemia and/or thrombocytopenia (Rai stages III or IV)
- d. Massive or progressive or symptomatic splenomegaly.
- e. Massive lymphadenopathy (at least 10 cm in the longest diameter) or progressive or symptomatic lymphadenopathy
- f. Progressive lymphocytosis with an increase of more than 50% over a 2 month period or lymphocyte doubling time (LDT) of less than 6 months. LDT can also be obtained as liner regression at 2 weeks intervals over an observation period of 2 to 3 months.
- g. Autoimmune anemia or thrombocytopenia that is poorly responsive to corticosteroids or other standard therapy
- h. Constitutional symptoms defines as: unintentional weight loss of 10% or more within the previous 6 months, significant fatigue (i.e, ECOG PS 2 or worse, inability to work or perform usual activities), fever higher than 100.5 °F (38.0 °C for 2 or more weeks without evidence of infection, night sweats.

Appendix B

ECOG Performance Status

Grade	Description
0	Normal activity. Fully active, able to carry on all pre-disease performance without restriction.
1	Symptoms, but ambulatory. Restricted in physically strenuous activity, but ambulatory and able to carry out work of a light or sedentary nature (e.g., light housework, office work).
2	In bed <50% of the time. Ambulatory and capable of all self-care, but unable to carry out any work activities. Up and about more than 50% of waking hours.
3	In bed >50% of the time. Capable of only limited self-care, confined to bed or chair more than 50% of waking hours.
4	100% bedridden. Completely disabled. Cannot carry on any self-care. Totally confined to bed or chair.
5	Dead.

*As published in Am. J. Clin. Oncol.: *Oken, M.M., Creech, R.H., Tormey, D.C., Horton, J., Davis, T.E., McFadden, E.T., Carbone, P.P.: Toxicity And Response Criteria Of The Eastern Cooperative Oncology Group. Am J Clin Oncol 5:649-655, 1982.* The Eastern Cooperative Oncology Group, Robert Comis M.D., Group Chair.

Appendix C

Response Criteria per International CLL Working Group

The International Workshop on Chronic Lymphocytic Leukemia (IWCLL) included updated response criteria in their 2008 publication [14].

The response categories are:

- **Complete remission (CR)**, requiring absence of peripheral blood clonal lymphocytes by immunophenotyping, absence of lymphadenopathy, absence of hepatomegaly or splenomegaly, absence of constitutional symptoms and satisfactory blood counts
- **Complete remission with incomplete marrow recovery (CRi)**, defined as CR above, but without normal blood counts
- **Partial remission (PR)**, defined as $\geq 50\%$ fall in lymphocyte count, $\geq 50\%$ reduction in lymphadenopathy or $\geq 50\%$ reduction in liver or spleen, together with improvement in peripheral blood counts
- **Progressive disease (PD)**, defined as $\geq 50\%$ rise in lymphocyte count to $> 5 \times 10^9/L$, $\geq 50\%$ increase in lymphadenopathy, $\geq 50\%$ increase in liver or spleen size, Richter's transformation, or new cytopenias due to CLL
- **Stable disease**, defined as not meeting criteria for CR, CRi, PR or PD

Ibrutinib and PD-1 Blockade to Improve Immune Dysfunction in
Chronic Lymphocytic Leukemia
Protocol <#>

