3 OBJECTIVES AND PURPOSE

Objective:

This is designed as a phase II study intended to evaluate the impact of sequential overlapping treatment with PD-1 monoclonal antibody (mAb), pembrolizumab/MK-1375, followed by ibrutinib on endogenous immune function in previously untreated, high-risk CLL patients (defined as presence of del17p or TP53, del11q or ATM mutation, unmutated IGVH or mutated IGVH with 3.21 phenotype) with absolute lymphocyte count >20,000 but without meeting iwCLL criteria to start therapy.

Primary Objectives:

1. Assessment of the complete response (CR) of CLL to therapeutic intervention (defined per current iWCLL 2008 response criteria)
2. Time to response of CLL to therapeutic intervention (defined as time to achievement of response according to iWCLL 2008 criteria).

Secondary Objectives

1. Assessment of the overall response rate (ORR) [CR + PR] per iWCLL 2008 response criteria
2. Restoration of immune response as measured by:
 - a. Decreased markers of T-cell exhaustion
 - b. Increased of quantitative immunoglobulin levels and subtype
2. Safety and toxicity of the combination
3. Progression free survival (PFS)
4. 3. Incidence of Richter's transformation (defined as transformation of CLL into an aggressive lymphoid/histiocytic histology including well defined World Health Organization 2008 subtypes). Richter's transformation should be biopsy proven

Exploratory Objectives:

1. Alterations in T lymphocyte function, including changes in:
 - a. TH1:TH2 polarization, and TReg:TH17 distributions
 - b. Markers of T cell exhaustion and/or inhibition
 - c. Alterations in distribution of naïve vs. memory
 - d. Cellular activation and cell-mediated cytotoxic capacity
2. Alterations in B lymphocyte function, including changes in:
 - a. Serum anti-pneumococcal antibody titers in response to Prevnar vaccination
 - b. Quantitative serum immunoglobulin levels and subtyping
 - c. Fc-receptor (FcR) expression patterns
3. Alterations in global systemic cytokine patterns: Includes IFN- γ , TNF- α , IL-2, IL-4, IL-10, IL-6, IL-17A, allowing discrimination between TH1, TH2, and TH17 profiles (described in Section 4.2.2.2)

Hypothesis for Primary and Secondary Objectives:

The therapeutic combination of PD1:PDL1 blockade (PDB) and ibrutinib can improve the severe immune dysfunction classically associated with CLL, thereby improving disease-related morbidity and mortality in high-risk, previously untreated patients.

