2. T cell function will be assessed for changes in multiple characteristics including memory formation, TH-polarity, markers of exhaustion, and activation via flow cytometric analysis. Naïve and memory subpopulations will be defined according to expression of CD45RA, CD62L, CCR5 and CCR7. TH-polarization, including TH1, TH2, TH17 and TReg subsets, will be determined by intracellular cytokine and FoxP3 profiles. Changes in T cell exhaustion phenotype will be tracked in terms of surface expression of several well-defined markers, including CD160, CD200R, CD244, CD272, CD274, CD279, as well as the intracellular markers Lag3 and Tim3. Alterations in cellular activation will be measured in terms of phosphorylation of critical T cell signaling pathways, STAT 1, 3 and 5, as well as by surface expression of CD107a, correlating to secretory/cytotoxic activity.
3. Humoral immunity will be monitored in terms of quantitative serum immunoglobulin levels as well as IgG subtyping by ELISA assay. FcR subtype utilization patterns will also be evaluated by flow cytometric means to identify potential alterations in cellular interpretation of antibody-mediated signaling.
4. Evaluation of MRD by 4-color flow cytometry. It will be performed in patients who achieved CR and PR per iwCLL criteria. If CBC with differential demonstrates the normalization of WBC to normal limits with no evidence of lymphocytosis, a peripheral blood sample will be obtained (within 14 days) to determine the MRD status of the CLL in peripheral blood by multiparameter flow cytometry. If MRD is negative, a confirmation of MRD status in the bone marrow will be performed at the discretion of the investigator.
5. Peripheral blood to collect DNA and RNA will be stored for future assessments.

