7.1.11 Assessment of Disease

Assessment of response (ORR) is a primary end point and will be reported using the latest Response Criteria Guidelines per the International Working Group of CLL. (Appendix C)

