7.1.15 Tumor Imaging

Tumor imaging will consist of CT scan of the neck, chest, abdomen and pelvis. CT scan will be done at screening (if not done within 3 months prior to consent). Response assessments will be done at week 12 (+/-3 days), week 24 (+/-3 days), and after 51 weeks of ibrutinib. If the subject discontinues treatment early or progression of disease is suspected, CT will be done at the discretion of the investigator. Imaging during follow-up will be performed per investigator discretion.

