7.1.16 Bone Marrow Biopsy

A bone marrow biopsy will be performed at screening (if not performed within 30 days), after the end of pembrolizumab and ibrutinib therapy (28-35 days after week 51). If subject discontinues treatment early or progression of disease is suspected, a bone marrow biopsy will be done at the discretion of the investigator. During follow-up, bone marrow biopsies will be performed per investigator discretion.

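### Appendix C defines complete response without any bone marrow item and no section links the scheduled post-treatment marrow to the CR call, so residual marrow CLL would not prevent a CR under that text

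*Combined protocol and SAP*

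**What the plan says.** Section 3 sets the first primary objective as "Assessment of the complete response (CR) of CLL to therapeutic intervention (defined per current iWCLL 2008 response criteria". The guideline itself is not reproduced. Section 7.1.11 says that response "will be reported using the latest Response Criteria Guidelines per the International Working Group of CLL. (Appendix C". Appendix C then defines CR as "requiring absence of peripheral blood clonal lymphocytes by immunophenotyping, absence of lymphadenopathy, absence of hepatomegaly or splenomegaly, absence of constitutional symptoms and satisfactory blood counts". CRi is named for incomplete marrow recovery, yet it is "defined as CR above, but without normal blood counts", so it too rests on blood counts.

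The marrow appears only as a procedure. Section 7.1.16 and footnote 11 of the Schedule of Events require it at screening and "after the end of pembrolizumab and ibrutinib therapy (28-35 days after week 51". For early stoppers, "If subject discontinues treatment early or progression of disease is suspected, a bone marrow biopsy will be done at the discretion of the investigator". Section 7.1.15 places the response readings under imaging: "Response assessments will be done at week 12 (+/-3 days), week 24 (+/-3 days), and after 51 weeks of ibrutinib". No marrow is planned at weeks 12 or 24. Section 4.1 leaves marrow MRD confirmation to the investigator, as a correlative study.

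Section 10.2.1 counts CRs in a Simon minimax design: null 10%, alternative 30%, stop if 1 or fewer of 16 respond, reject the combination if 4 or fewer of 25 respond.

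**The concern.** Section 2.1 describes CLL as accumulating in the bone marrow among other sites, and patients undergo a biopsy there after treatment. Yet the written definition of the primary endpoint does not use the result. A marrow showing persistent CLL would leave all the Appendix C items met, and so the CR label intact.

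The final cut-off lies between 4 and 5 CRs in 25, so one or two such patients can change the trial's conclusion. The same patients also make it easier to pass the stage-1 look. The bias runs one way: towards accepting a combination whose marrow-clear CR rate is no better than the null. In addition, two assessors could classify the same patient differently, depending on whether each relied on Appendix C or went back to the cited guideline.

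**Working it through.** **Step 1: the text.** The items needed for CR in Appendix C, set against where each is measured:

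| Item | In the CR definition? | Where measured |
|---|---|---|
| Blood immunophenotype | yes | Section 4.1, item 4 (flow) |
| Nodes, liver, spleen | yes | CT, Section 7.1.15; physical examination |
| Constitutional symptoms | yes | clinic visits |
| Blood counts | yes | hematology |
| Bone marrow | no | Section 7.1.16, 28-35 days after week 51 |

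No section connects the last row to the response call.

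**Step 2: reproduce the design.** Inputs from Section 10.2.1: n1 = 16, r1 = 1, n = 25, r = 4, p0 = 0.10, p1 = 0.30.

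- Early termination at p: PET(p) = (1-p)^16 + 16p(1-p)^15. At 0.10 this is 0.1853 + 0.3294 = 0.5147 (the plan states 0.52).
- Expected size: 16 + 9 × (1 - 0.5147) = 20.37, as stated.
- Success at p: the sum over x = 2 to 16 of P(X1 = x) × P(X2 ≥ 5 - x), with X1 ~ Bin(16, p) and X2 ~ Bin(9, p). This gives 0.0951 at 0.10 and 0.9030 at 0.30, consistent with the stated 10% and 90%.

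A full search for the minimax design at these error rates returns the same 16/1 and 25/4 rule. The stated 0.52 against 0.51 is immaterial.

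**Step 3: illustration of the effect.** Assume that the marrow-clear CR rate is exactly 10%, that the 10% null means marrow-clear CR, and that a further m of all patients are marrow-positive but meet Appendix C. The documents give no value for m, so a range is shown. The rule then operates at 0.10 + m.

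| m (points) | Apparent CR rate | Share of apparent CRs that are marrow-positive | P(early stop) | P(declare success) |
|---|---|---|---|---|
| 0 | 10% | 0 | 0.515 | 0.095 |
| 2 | 12% | 2/12 = 17% | 0.412 | 0.169 |
| 5 | 15% | 5/15 = 33% | 0.284 | 0.310 |
| 10 | 20% | 10/20 = 50% | 0.141 | 0.569 |

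In 25 patients, 5 points is 25 × 0.05 = 1.25 patients and 10 points is 2.5.

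**Step 4: can stage 1 use CRs not yet confirmed by marrow?** The marrow falls at week 51 + 28/7 = 55 to 51 + 35/7 = 56, so a confirmed stage-1 count would wait that long after the sixteenth patient starts. Suppose stage 1 counts unconfirmed CRs and the final count uses confirmed ones.

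- The chance of success cannot exceed that with no stage-1 stopping: P(at least 5 of 25) = 0.098 at 10% and 0.910 at 30%.
- It cannot fall below the step 2 values (0.095 and 0.903), provided every confirmed CR among the first 16 is already counted as unconfirmed at the look.

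Type I error therefore stays at or below 0.098, and power at or above 0.90 under that proviso. Early termination and expected size do change. With an unconfirmed rate of 15%, for example, they are 0.284 and 16 + 9 × 0.716 = 22.44.

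**The case against.** The strongest reply is that Appendix C is a summary. The objectives define CR by iwCLL 2008, Appendix C cites that publication as its source, and an assessor who applies it directly might use the marrow. The Section 7.1.11 sentence that points to Appendix C also names ORR rather than CR. This stands as a limit on certainty: one can say only that such a patient would count as CR under Appendix C as written. It does not cure the gap, because Section 7.1.11 asks for the most recent criteria, Section 3 and Appendix C name the 2008 ones, and no precedence is given.

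A second reply is that the inflation is hypothetical. That is correct. If the 10% and 30% describe CR as Appendix C has it, the type I error is still 0.095. Section 10.2.1 does not say which CR they describe.

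Two stronger readings are tempting and are not supported:

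- A reader might infer that the flow rule is circular, since CR needs blood immunophenotyping while Section 4.1 says of MRD flow that "It will be performed in patients who achieved CR and PR per iwCLL criteria". But the next sentence there also triggers a blood flow sample within 14 days once the white count normalises without lymphocytosis. Moreover, PR in Appendix C needs no flow, so a candidate for CR can reach the test as a PR. At most, the test lacks its own row in the Schedule of Events.
- A reader might infer that the biopsy is meant to serve no endpoint. The documents are silent on its use; they do not exclude it from response assessment.

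**Conclusion.** The point holds as a defect in the primary endpoint's definition. The only spelled-out CR rule omits the marrow, and the scheduled post-treatment marrow has no stated role in the CR call. A patient with residual marrow CLL who meets the listed items would be a CR under Appendix C as written, in the count that decides the trial.

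The direction of the effect is clear; its size is not known. A rise in the chance of success from 0.095 to 0.31 or 0.57 needs 5 or 10 points of marrow-positive CRs, which is a third or a half of all apparent CRs, and a null that means marrow-clear CR. Both are assumptions. The Simon design itself reproduces and is not in question.

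**What to change.** In Appendix C:

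- Define CR for the final primary analysis as the listed items plus no CLL on the post-treatment marrow already scheduled.
- Count a patient who is otherwise clear but has a positive or missing marrow as PR, and report that group separately as unconfirmed CR.
- State which criteria version governs, since the text names both the 2008 and the most recent one.

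In Section 10.2.1, state that the 10% and 30% refer to this CR. If stage 1 will count unconfirmed CRs, say so, and note that the stated early-termination probability (0.52) and expected sample size (20.37) then no longer apply exactly, while type I error stays at or below 0.098 and power at 30% at or above 0.90 under the proviso in step 4.

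Two small items go with it. List the blood flow test in the Schedule of Events at response visits. Reconcile the marrow timing: Section 7.1.16 gives 28-35 days after week 51, Section 7.3.2.11 lists the biopsy at a visit 0-7 days after the last dose, and Section 6.1.9 allows pembrolizumab to run for up to 2 years.

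The cost is wording; both procedures are already planned and the sample size does not change. The downside is a somewhat lower reported CR rate, and early stoppers without a marrow cannot be CR.
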